  - 9 The first time the patient tested positive for COVID-19 will be included as well. The test will be repeated in the 48 hours prior to administration of plitidepsin and on days 4, 7, 15 and 31, if negative detection does not occur before then. Qualitative PCR shall be obtained on nasopharyngeal exudate (preferably) or a sample from the lower respiratory tract.
  - 10 A chest X-ray will be performed at baseline and subsequently based on clinical discretion.
  - 11 Only fertile women.
  - 12 Patients may receive other pharmacological treatments for COVID-19 at the discretion of the investigator 24 hours after administration of the last dose of plitidepsin.
  - 13 Adverse events (serious and non-serious) will be recorded from signing of the informed consent up to 28 days after administration of the last dose of plitidepsin.
  - 14 A safety visit will be made 28 days (+3 days) after the last dose of plitidepsin.
  - 15 The viral load should be determined in a sample obtained from nasopharyngeal exudate (preferably) or a sample from the lower respiratory tract.

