## **12.5. Analysis of secondary endpoints**

### **12.5.1. Efficacy assessments**

Efficacy analyses will be performed on the efficacy population defined above. For the evaluation of efficacy endpoints, the following analyses will be carried out separately for each dosage level:

- The evolution of the viral load from the baseline visit on days 3, 4, 7, 15 and 31 will be provided.
- The time to negative detection of COVID-19 by PCR will be calculated as the time that elapses in days from the date of randomisation to the first date of PCR with a negative result. The time to negative detection will be analysed following the Kaplan-Meier methodology, providing the median and the corresponding 95% confidence interval.
- The number and percentage of patients who die 7, 15 and 31 days after starting the treatment with plitidepsin shall be described.
- The number and percentage of patients who require mechanical ventilation and/or ICU admission at 7, 15 and 31 days will be provided.
- The number and proportion of patients requiring invasive mechanical ventilation shall be stated.
- The number and proportion of patients requiring non-invasive mechanical ventilation shall be stated.
- The number and proportion of patients requiring oxygen therapy shall be stated.

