Intra-patient dose change/increase is not allowed.

Once the 27 patients (9 in each dose level) will be included, an extension period to include 18 additional patients (6 in each plitidepsin dose level) to expand the collection of safety information for the different doses and to collect efficacy data will be performed. After this extension period, data will be available from 15 patients at each plitidepsin dose level. During the extension period, patients will be randomized by 1:1:1 ratio.

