 - Moderate and Mild Patients following the FDA Classification
 - Moderate patients following the FDA Classification

b) COVID-19 evolution by PCR:

For the analysis of COVID-19 evolution by PCR, the number and percentage of patients who have taken the PCR test will be indicated at the baseline and at visit 4, 7, 15 and 31 describing the results (positive / negative) in those patients.

A list of PCR evolution of the patients from baseline to the last visit will be presented.

c) Time to negative detection of COVID-19 detection by PCR:

The time to negative detection of the detection of COVID-19 by PCR is defined as the time, in days, from the date of baseline PCR to the first PCR date with a negative result and does not have a positive result in the following PCR or having a negative result in the last PCR date (Day 31).

The following analyses will be presented.

The time to negative detection will be analyzed by the Kaplan-Meier method and the median and the 95% confidence interval will be provided.

- The number and percentage of patients with qualitative PCR at 4, 7, 15 and 31 days
- A descriptive table will be provided in which both variables are related to each of the variables indicated below:
 - Chronic lung disease (excluding asthma) (Yes; No).
 - Oxygen therapy on day 1 (Yes; No).
 - Plitidepsin dose
 - Days from symptoms until 1st dose of plitidepsin
 - Baseline severity of the disease
 - Age
 - Sex
 - Use of corticosteroids
 - Race
 - Use of other antivirals or other specific treatments for COVID 19

d) Deaths:

The number and percentage of patients who die within 7, 15 and 31 days after starting the treatment with plitidepsin will be described.

- From day 1 to day 7
- From day 8 to day 15
- From day 16 to day 31

In addition, cumulative table will be presented with the following groups:

- From day 1 to day 7
- From day 1 to day 15
- From day 1 to day 31

e) Oxygen therapy:

The number and percentage of patients requiring oxygen therapy on days 7, 15 y 31 after the start of plitidepsin treatment.

- From day 1 to day 7
- From day 8 to day 15
- From day 16 to day 31

In addition, cumulative table will be presented with the following groups:

- From day 1 to day 7
- From day 1 to day 15
- From day 1 to day 31

A descriptive table will be provided in which both variables are related to each of the variables indicated below at 4, 7, 15 and 31 days:

- Chronic lung disease (does not include asthma) (Yes; No).

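### Time to negative PCR is interval-censored, but the Kaplan-Meier analysis takes the test date as the exact event date, so the median is tied to the visit calendar and biased late

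*SAP*

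**What the plan says.** Protocol 10 (evaluation calendar, footnote 9) schedules qualitative PCR at baseline and then "on days 4, 7, 15 and 31, if negative detection does not occur before then". SAP 8.1 b tabulates the same tests: "at the baseline and at visit 4, 7, 15 and 31". The calendar allows a window of ±1 day for Day 15 and ±3 days for Day 31.

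The two documents start the clock at different points. SAP 8.1 c counts "from the date of baseline PCR to the first PCR date with a negative result" and adds a condition that no positive follows. Protocol 12.5.1 counts "from the date of randomisation to the first date of PCR with a negative result". For the baseline PCR, footnote 9 says: "The test will be repeated in the 48 hours prior to administration of plitidepsin".

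The method is the same in both. The SAP says "The time to negative detection will be analyzed by the Kaplan-Meier method and the median and the 95% confidence interval will be provided", and the Protocol has the endpoint "analysed following the Kaplan-Meier methodology, providing the median and the corresponding 95% confidence interval". Neither mentions interval censoring, an estimator for it or a sensitivity analysis, and SAP 4.6 foresees no imputation.

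Test-date times are used elsewhere too. SAP Table 12.1.11 compares time to negative detection across doses and other factors by Kruskal-Wallis. Table 12.1.7 gives a mean time from baseline until undetectable viral load, which is measured at the same visits.

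**The concern.** A patient who is positive on Day 7 and negative on Day 15 cleared at some point in an 8-day interval. Kaplan-Meier on test dates puts the event at the end of that interval, and does so for every patient. Three things follow:

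- The median and its confidence limits can take only values that the visit calendar allows.
- The estimate is late by up to the width of an interval.
- A difference between doses can vanish inside one interval, or be enlarged when it straddles a visit.

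The endpoint is a named secondary endpoint. It is part of the efficacy data that the sponsor and the Spanish agency will weigh with safety when they choose the dose, and each arm is small: "data will be available from 15 patients at each plitidepsin dose level".

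**Working it through.** Neither document gives an expected median, effect size or power for this endpoint, so there is no planned figure to reproduce.

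**Step 1. Gaps between scheduled tests.** Day 4 to 7: 7 − 4 = 3 days. Day 7 to 15: 15 − 7 = 8 days. Day 15 to 31: 31 − 15 = 16 days nominally, and from 28 − 16 = 12 to 34 − 14 = 20 days with the windows.

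**Step 2. Event times that scheduled tests can produce on the SAP clock.** The first dose is on Day 1 and the baseline PCR is 0 to 2 days before it. The event time is therefore (visit day − 1) + window + (0 to 2).

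| Visit | Earliest | Latest |
|---|---|---|
| Day 4 | 3 + 0 = 3 | 3 + 2 = 5 |
| Day 7 | 6 + 0 = 6 | 6 + 2 = 8 |
| Day 15 (±1) | 14 − 1 + 0 = 13 | 14 + 1 + 2 = 17 |
| Day 31 (±3) | 30 − 3 + 0 = 27 | 30 + 3 + 2 = 35 |

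No scheduled test can give a time of 9-12 or 18-26 days. The Kaplan-Meier median, taken as the first time at which the curve is at or below 0.5, is an observed event time and so must lie in one of the four clusters. This step rests on the calendar alone.

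**Step 3. Size of the late bias.** This step needs assumptions. Time to negative is taken as Weibull with shape 1.5. Baseline PCR is 0 to 2 days before dosing, and visits are uniform within their windows. No test is missed, n = 15, and there are 1,000 simulated arms per row.

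| True median (days) | Mean reported median | Reported in 6-8 | Reported in 13-17 | Reported in 27-35 |
|---|---|---|---|---|
| 5 | 7.0 | 75% | 8% | 0% |
| 8 | 12.4 | 27% | 72% | 0% |
| 10 | 14.6 | 10% | 86% | 4% |
| 12 | 17.5 | 2% | 80% | 17% |
| 18 | 26.6 | 0% | 24% | 76% |
| 20 | 28.2 | 0% | 15% | 85% |

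Most of the remainder in each row lies at 3-5 days. More patients do not help: with n = 45 and a true median of 10, the mean reported median is 14.8.

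**Step 4. Effect on comparing doses.** With shape 1 or 1.5:

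- Two arms with the same true median of 8 days have reported medians at least 5 days apart in 41-49% of trials. If times were exactly observed, the figure would be 7-23%.
- Arms with true medians of 8 and 14 days are both reported at 13-17 in 33-43% of trials.

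**Step 5. What an interval-censored estimator changes.** With nominal timing and no missed test, the intervals (0,4], (4,7], (7,15] and (15,31] do not overlap. The Turnbull estimate then gives the same cumulative proportion at each visit as Kaplan-Meier. What changes is the median: a result that Kaplan-Meier prints as 15 becomes (7,15], which no longer places the event at the late end. In large samples, true medians of 8 and 14 both read (7,15], and true medians of 6 and 8 read (4,7] and (7,15]. A parametric interval-censored Weibull fit did recover the medians (7.9 and 9.7 for true values of 8 and 10), but it fitted the same family that was simulated, so it is a best case.

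**The case against.** The strongest defence is that the endpoint is defined as time to the first negative test, and that date is observed. On that reading Kaplan-Meier estimates what was defined, and a footnote would suffice. This stands as far as it goes. But the objective is stated as efficacy, and a median in days with a 95% CI will be read as time to clearance. A footnote would not help the Table 12.1.7 mean or the Table 12.1.11 p-value.

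A second defence is that per-visit results are already planned: negative or undetectable viral load by visit and dose (SAP 8.1 a, Table 12.1.9) and qualitative PCR by visit and dose (Table 12.1.1). Protocol 12.1 foresees exact 95% intervals for relevant categorical variables. This reduces the reliance on the median. However, these are not cumulative proportions. PCR testing stops after a negative result, and SAP 3 leaves missing values out of the percentages, so patients already negative can drop out of later denominators. SAP Table 12.1.6 names exact intervals only for ventilation and ICU.

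Third, all arms share one schedule, so no dose is systematically favoured. That is correct.

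Two stronger readings are tempting. A reader might infer that the median can only be 4, 7, 15 or 31. That holds only on an idealised study-day clock without windows. On the SAP clock, exactly those values arose in only about 22-41% of simulated arms. A reader might also infer that an interval-censored estimator would reveal dose differences hidden inside an interval. Step 5 shows that a nonparametric one cannot, because the limit is the visit schedule.

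**Conclusion.** The concern holds in this form: the data are interval-censored, both documents treat the test date as exact, and the reported median falls in one of four visit clusters and is biased late. The clustering follows from the calendar. An unscheduled PCR, which the documents neither plan nor exclude, could add other values.

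The size of the bias depends on the assumed distribution. Under the Step 3 assumptions it is 12.4 − 8 = 4.4 days at a true median of 8, 14.6 − 10 = 4.6 days at 10, and 26.6 − 18 = 8.6 days at 18.

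A reader might infer that a formal test or the dose decision is invalidated. The documents do not support that. SAP 1 makes the final analysis descriptive, this endpoint carries no alpha or power, and dose selection rests on joint review of all safety and efficacy data, with no rule tied to this median. What is affected is the reported median, its confidence interval and the informal comparison of doses. It should be changed, but it does not undermine the trial.

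**What to change.** Amend SAP 8.1 c as follows:

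1. Use the Turnbull nonparametric estimator on the interval (last positive test, first qualifying negative test]. Patients never negative are right-censored at their last positive test. State one time origin, because the Protocol and SAP now differ. Say what makes a negative qualify when footnote 9 stops testing after the first one.
2. Report the median as an interval.
3. Make the cumulative proportion negative by Days 4, 7, 15 and 31, per dose with 95% CI, the main summary.
4. Treat time to undetectable viral load in the same way, replacing the mean time in Table 12.1.7.
5. In Table 12.1.11, replace Kruskal-Wallis with an interval-censored comparison, or label it as a comparison of test dates.
6. State that this removes the late bias and the false precision, and handles missed tests and windows, but cannot separate doses whose difference lies within one visit interval.

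The cost is SAP wording and one added procedure, with no new visits, samples or patients. The result will look less precise than a single-day median.

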4.6 Missing data

Missing data imputation is not foreseen.

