- Total patients requiring ICU (95% IC)
- Number and percentage of patients requiring ICU admission since the start of treatment with plitidepsin.
 - From day 1 to day 7
 - From day 8 to day 15
 - From day 15 to day 31
- In addition, cumulative table will be presented with the following groups:
 - From day 1 to day 7
 - From day 1 to day 15
 - From day 1 to day 31
- A descriptive table in which this variable is related to each of the variables indicated below at 4,7, 15 and 31 days from the start of treatment will be provided:
 - Chronic lung disease (does not include asthma) (Yes; No).
 - Oxygen therapy at baseline (Yes; No).
 - Days from onset of symptoms (continuous)
- Time in ICU admission (continuous): The time in ICU is defined as the time, in days, from ICU admission to ICU discharge. It will be only calculated for those patients who have been admitted and discharged from the ICU.
- Onset day of ICU admission (continuous): Onset day of ICU admission is defined as the time, in days, from the date of the first dose of plitidepsin treatment to the date of admission to the ICU. It will only be calculated for those patients who have been admitted to the ICU.
- Use of corticosteroids and/or antiviral and other specific COVID 19 treatments
- Time from ICU admission to Hospital discharge (continuous): The time from ICU admission is defined as the time, in days, from the date of ICU admission to the date of discharge from the center. It will only be calculated for those patients who have been admitted and discharged from the ICU and have also been discharged from the center. Reason for ICU discharge (taken back to the ward; Death; Others).
- Invasive mechanical ventilation (Yes; No).
- Non-invasive mechanical ventilation (Yes; No).
- High flow oxygen therapy (Yes; No).

k) ICU admission or Mechanical ventilation (Invasive):

The following analysis will be performed:

- Number and percentage of patients requiring invasive mechanical ventilation or ICU admission since the start of treatment.
 - From day 1 to day 7
 - From day 8 to day 15
 - From day 16 to day 31
- In addition, cumulative table will be presented with the following groups:
 - From day 1 to day 7
 - From day 1 to day 15
 - From day 1 to day 31

l) Hospitalization:

The following variables will be analyzed:

- Hospital discharge (Yes / No). If not, a list of reasons will be provided.

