- Time to Hospital discharge (continuous): The time to Hospital discharge is defined as the time, in days, from the date of treatment start and the date of hospital discharge. In those patients who have not been discharged, the time, in days, from the date of first dose to the last available date will be calculated and it will be censored for time to event analyses. The description of the variable will be done separately depending on whether the patient has been discharged from hospital or not. The median and 95% confidence interval will be presented.
- Time from admission to Hospital discharge (continuous): The time to Hospital discharge is defined as the time, in days, from the date of admission and the date of hospital discharge
- Multivariate analysis will be done to evaluate the relationship of the main covariates in the analysis with Hospital discharge on Day 8 (Yes/No) and Hospital discharge on Day15 (Yes/No) by means of logistic regression models. More relevant exploratory covariates from the univariate analyses (p-value < 0.10) will be included in the multivariate analyses.
- Multivariate analysis will be done to evaluate the relationship of the main covariates in the analysis with time to hospital discharge by means of Cox proportional hazard models. More relevant exploratory covariates from the univariate analyses (p-value < 0.10) will be included in the multivariate analyses.
- Swimmer plot Hospital Discharge Day by Viral Load at Baseline, Disease Severity at Baseline and oxygen (yes/no) at baseline.

m) Class at discharge:

The time to hospital discharge (category 1) at 6-points ordinal scale will be analyzed by the Kaplan-Meier method and the median and the 95% confidence interval will be provided.

The analysis will be completed by the following subgroups:

- FDA classification
- Oxygen therapy on day 1
- Symptoms evolution less or equal/greater than 6 days.

The value of the 6-point ordinal scale will be derived from CRF data by using the following definition:

1. Discharge (Alive)
2. Hospital admission, not requiring supplemental oxygen.
3. Hospital admission, requiring supplemental oxygen.
4. Hospital admission, requiring high-flow nasal cannula or non-invasive mechanical ventilation.
5. Hospital admission, requiring extracorporeal membrane oxygenation or invasive mechanical ventilation.
6. Death.

In addition, the following analyses will be performed:

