High >7				
Total				

Table 12.1.11 Time to negative detection

Time to negative detection	Time to negative detection			p-value(**)
	N	Median	Range	
Viral load at baseline				
Low <4				
Medium [4-7]				
High >7				
Dose				
1.5 mg				
2.0 mg				
2.5 mg				
Age				
< 65 y.o.				
>=65 y.o.				
Sex				
Female				
Male				
Race				
White				
Other				
... (*)				

(*) FDA risk groups (Mild, moderate, severe), Oxygen need (Yes/No), Chronic lung disease (Yes/No), Corticosteroids (Yes/No), Other antiviral treatment for COVID-19 (Yes/No). Further variables could be added upon request

(**) Kruskal-Wallis

Table 12.1.12 Time to negative detection by corticosteroid duration

Time to negative detection	Corticosteroid duration		p-value*
	< 10 days	>= 10 days	
Dose			
1.5 mg			
2.0 mg			
2.5 mg			
Total			

(**) Kruskal-Wallis

Table 12.1.13 Oxygen therapy

Number of patients (%)	Dose Cohort							
	1.5 mg N=X		2.0 mg N=X		2.5 mg N=X		Total N=X	
	Oxygen therapy							
	Yes	No	Yes	No	Yes	No	Yes	No
Oxygen therapy at baseline								
Yes								
No								
Chronic Lung Disease								
Yes								
No								
Age								
< 65 y.o.								
>=65 y.o								
Gender								
Female								
Male								
Race								
White								
Other								
Viral load at baseline								
Low <4								
Medium [4-7]								
High >7								
FDA Risk groups								
Mild								
Moderate								
Severe								

Listing 12.1.14 Oxygen therapy evolution

Subject id	Dose	Visit	Date	Time	Oxygen therapy type	Flow

Table 12.1.15 Oxygen therapy onset day

Onset day	Dose Cohort							
	1.5 mg N=X		2.0 mg N=X		2.5 mg N=X		Total N=X	
From start of symptoms								
From first plitidepsin dose								
From corticosteroids use								

Table 12.1.16 Patients changing oxygen therapy

	Dose Cohort			
	1.5 mg N=X	2.0 mg N=X	2.5 mg N=X	Total N=X
From no Oxygen therapy to Oxygen therapy				
From low flow to high flow				
From high flow to low flow				

Table 12.1.17 Time in (ICU- Invasive M Ventilation – Non Invasive MV – in Hospital)

Time (days)	Dose Cohort			
	1.5 mg N=X	2.0 mg N=X	2.5 mg N=X	Total N=X
ICU				
Invasive mechanical ventilation				
Non Invasive mechanical ventilation				
Hospital*				

(*)From first infusion

Table 12.1.18 Reason for ICU discharge

Endpoint	Dose Cohort			
	1.5 mg N=X	2.0 mg N=X	2.5 mg N=X	Total N=X
Reason for ICU discharge, n (%)				
Taken back to the ward				
Death				

Table 12.1.19 ICU admission according to oxygen therapy or chronic lung disease

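### Time in ICU omits stays still open at last follow-up and counts a death in ICU as a completed stay

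*SAP*

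**What the plan says.** SAP 8.1 j) gives the definition: "The time in ICU is defined as the time, in days, from ICU admission to ICU discharge". It then limits who is counted: "It will be only calculated for those patients who have been admitted and discharged from the ICU". A few lines later it lists the possible ends of an ICU stay: "Reason for ICU discharge (taken back to the ward; Death; Others". The shell headed "Table 12.1.18 Reason for ICU discharge" has a row for death as well as one for return to the ward.

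Table 12.1.17 shows ICU time by dose cohort and in total. It has no split by how the stay ended, no row for stays that have not ended, no count of contributing patients beyond the cohort N, and no named statistic. SAP section 3 supplies the default for continuous variables: mean, median, standard deviation, range and quartiles. SAP 4.6 adds: "Missing data imputation is not foreseen".

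Hospital stay is treated differently. In SAP 8.1 l) a patient not discharged is given the time from first dose to the last available date, which "will be calculated and it will be censored for time to event analyses", and discharged and undischarged patients are described separately. The ordinal scale in SAP 8.1 m) reserves its best category for patients discharged alive.

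For invasive and non-invasive ventilation, SAP 8.1 h) and i) measure duration from first use to removal. They neither restrict the calculation to completed episodes nor say what happens on death or with ongoing use.

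**The concern.** A duration summary should not look better because patients did worse. Under the ICU rule it can, in two ways. A patient who has not left the ICU by last follow-up disappears from the calculation. A patient who dies soon after ICU admission supplies a short stay that cannot be told apart, in Table 12.1.17, from a quick recovery.

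Open stays are foreseeable. The last scheduled contact is about Day 31 (Protocol section 10: "A safety visit will be made 28 days (+3 days) after the last dose of plitidepsin"), and Protocol 5.2 itself describes long intensive-care stays in Madrid. At stake is the reading of one descriptive row by dose, in a trial whose safety and efficacy data are reviewed jointly to choose a dose.

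**Working it through.** The documents give no expected ICU rate, ICU stay or precision for this variable, so there is no planned figure to reproduce. The check is a reading of the rule, then its size under stated assumptions.

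**1. The rule applied to each outcome**

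| Outcome in ICU | Value under SAP 8.1 j) | SAP treatment of hospital stay |
|---|---|---|
| Left ICU alive | Admission to discharge | Time to discharge |
| Died in ICU | Admission to death, since death is a discharge reason | Best ordinal category requires discharge alive |
| Still in ICU | None | Time to last available date, censored |

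**2. How many ICU patients to expect**

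Inputs: 15 patients per arm and 45 in total (Protocol 6.1). The ICU rate is assumed at 5%, 10% and 20%. Protocol 5.2 quotes close to 10% needing mechanical ventilation in Madrid; this is only a stand-in for an ICU rate.

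- Per arm: 15 × 0.05 = 0.75; 15 × 0.10 = 1.5; 15 × 0.20 = 3.0.
- In total: 45 × 0.05 = 2.25; 45 × 0.10 = 4.5; 45 × 0.20 = 9.0.
- Chance of two or more ICU patients in an arm at 10%: 1 − 0.9^15 − 15 × 0.1 × 0.9^14 = 1 − 0.206 − 0.343 = 0.451.

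At 10%, an arm is more likely than not to have at most one ICU patient.

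**3. Illustration with assumed data**

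Five ICU patients: live discharge after 5, 8 and 12 days, one death on ICU day 2, one still in ICU at 24 days.

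- SAP rule, {2, 5, 8, 12}: mean 27/4 = 6.75, median 6.5, from four of five patients.
- Live discharges only, {5, 8, 12}: mean 25/3 = 8.3, median 8.
- Live discharges plus the open stay at its minimum, {5, 8, 12, 24}: mean at least 49/4 = 12.25, median 10, with the death reported separately.
- Death moved from ICU day 20 to day 2: the SAP median falls from 10 to 6.5 and the mean from 45/4 = 11.25 to 6.75. The earlier death gives the shorter stay.

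**4. Simulation under assumptions that are not in the documents**

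One million draws: ICU admission uniform over days 2 to 10, follow-up to day 31, survivors' stay exponential, time to ICU death exponential with mean 5 days.

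| Survivors' mean stay | ICU deaths | Stays dropped | Mean by SAP rule | Median by SAP rule | Survivors' true mean / median |
|---|---|---|---|---|---|
| 8 days | 40% | 3.1% | 6.00 | 4.35 | 8.0 / 5.5 |
| 12 days | 0% | 12.7% | 8.44 | 6.90 | 12.0 / 8.3 |
| 12 days | 20% | 10.3% | 7.63 | 5.89 | 12.0 / 8.3 |
| 12 days | 40% | 7.9% | 6.88 | 5.06 | 12.0 / 8.3 |
| 24 days | 0% | 35.4% | 10.38 | 9.34 | 24.0 / 16.6 |

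Hand check of the second row: the share dropped is (12/8) × [exp(−21/12) − exp(−29/12)] = 1.5 × (0.1738 − 0.0892) = 0.127.

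The no-death rows show that dropping open stays is enough to lower the summary. Across the 12-day rows, more deaths lower it further.

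**5. Patients dropped in the whole trial**

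At a 10% ICU rate and the 12-day, 20%-death case: 4.5 × 0.103 = 0.46. Over all simulated cases: 4.5 × 0.031 = 0.14 to 4.5 × 0.354 = 1.6.

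**The case against.** The strongest reply is that little depends on this row. ICU time is a descriptive addition with no test or decision rule, and the protocol endpoint is a percentage that this definition does not touch. Deaths can be seen by dose in Table 12.1.18 and in the death tables, ICU admissions are counted by arm, and the six-point scale ranks death worst. All of that stands and limits the importance. It does not repair Table 12.1.17, where a death and a live discharge remain mixed and open stays leave no trace.

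Four stronger readings are tempting, and the documents do not support them.

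- *The longest stays are dropped.* Only stays still open at last follow-up are dropped; long completed stays are kept. Whether an ICU discharge after Day 31 is recorded is not stated. Tables 12.1.4 and 12.1.5 have a row for deaths after Day 31, so a patient in ICU on that day is not necessarily lost.
- *The ventilation durations follow the same rule.* They do not. SAP 8.1 h) and i) are silent on death and ongoing use, which is a gap rather than a stated restriction.
- *About four or five patients are affected.* The figure 45 × 10% = 4.5 estimates patients needing ventilation, not those dying in ICU or still there. The 10% is also a background rate, and this trial excludes patients who are ventilated or in multi-organ failure at entry.
- *Dose ordering could be reversed by the rule.* With about 1.5 ICU patients expected per arm, ordering doses by ICU time is uninterpretable under any definition.

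It is also fair to say that no sentence states outright that time to death counts as a stay. That follows from death being listed as a reason for discharge.

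**Conclusion.** The point holds as a minor one. The SAP states a rule for ICU time that omits open stays and treats death in ICU as discharge. Omitting open stays biases the summary downward. Including deaths lowers it when they come early, as the simulation assumes; a late death can raise it, as the day-20 case shows. In either case the number then mixes recovery with death.

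The size is uncertain. The simulated shortfall ranges from a reported mean of 6.0 days against 8 to one of 10.4 against 24, and rests wholly on assumed stays, admission days and death rates. The number of dropped patients is probably small, 0.14 to 1.6 in the trial at a 10% ICU rate. With 0.75 to 3 ICU patients per arm, however, a single one can determine an arm's figure. The protocol endpoint and the death counts are unaffected.

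**What to change.** In Table 12.1.17, state the number of patients contributing and report ICU time in three rows per dose:

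- discharged alive from ICU: admission to discharge;
- died in ICU: admission to death;
- still in ICU: admission to the last available date, marked as censored.

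Amend SAP 8.1 j) to match. This extends the method that SAP 8.1 l) already uses for hospital stay. Because SAP 8.1 h) and i) give no rule for death or ongoing ventilation, add the same split there.

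ICU-free days to Day 31 are optional and not needed. If about 90% of patients never enter ICU, the measure sits near its ceiling. It would also need a rule for patients with less than 31 days of follow-up, since the efficacy population requires only two weeks.

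The dates are already needed for the planned tables, so no new assessments are required. The cost is a few extra rows with very small counts.
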